The study is being conducted at the Faculty of Health Science, Cumberland Campus of The University of Sydney, NSW, Australia. Training sessions and measurements are conducted on-site, while X-ray films are acquired at the Radiology Department of Concord Repatriation Hospital, Concord, NSW, Australia. Figure 1 shows the flowchart of the study design.

Sample size estimation

Sample size estimates have been calculated to test the hypothesised differences between the experimental and control conditions for the primary outcome (KAM). A weight loss of about 1 kg has been shown to decrease the peak knee adduction moment (KAM) by 0.496Nm [24]. Therefore, the control group change is based on the lifestyle advice-only control group weight loss of 1.1 kg (=KAM reduction of -

0.55 Nm) in the ADAPT trial [10]. Gait retraining benefit is estimated as the average of effects achieved in the literature: Mundermann 2007 (-65%), Fregly 2007 (-39%) [17, 29] and in our pilot 4-week trial (-55%). We acknowledge potential imprecision due to the fact that these published trials included only healthy participants, and our pilot data in 10 participants with OA (the GO study) was limited to 8 sessions over 4 weeks. However, as THE LO study is 12 months rather than 4 weeks in duration, we believe our estimate is conservative. PRT benefit is conservatively estimated as a 10% reduction, similar to the result seen in healthy subjects over 12 weeks [22]. It is expected that the Diet group will reduce their weight by at least 8.9kg as seen in the IDEA study [30]. Again this is a conservative estimate, as the novel High Protein/Low GI diet we are prescribing has been shown to be more effective than typical low fat, energy restricted diets such as that used in the IDEA study [25, 30, 31]. The values used for the KAM at baseline and the Standard Deviation (SD) for the effect size (ES) estimates are taken from the baseline of our pilot study of gait retraining (GO Study).

We have conservatively assumed a less than additive benefit when all three treatments are combined, as shown in Table 1, as they may be working through overlapping pathways to some degree. As there is no similar study in the literature, we have estimated the hypothesised change for the combined group as equal to Diet plus Gait Effect Size (ES 1.63). The sample sizes (n) required with alpha 0.05 and beta at 0.2 for each of the treatment arms is shown in Table 1.

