Therefore, 12 people per group would be required for Gat vs. Control hypothesis

testing with allocation of 1:1:1:1:1 for the 5 groups =n of 60 with a 40% dropout we need to recruit 100 participants. However, we will recruit an additional 25 people in the event that there is greater heterogeneity in our cohort than anticipated, due to the inclusion of men and women as well as a broad age range from middle aged to older adults compared to the literature on which the sample size estimates were derived.

We have powered the study to look at the effects of the 2 most novel interventions in THE LO study compared to control group (the two which have never been tested in this cohort): Gait vs. Control (ES= 1.25) and Combined vs. Control (ES= 1.63) as well as Combined vs. Diet (ES= 1.30) and Combined vs. PRT (ES=1.43)

With this sample size of 125, we will also be able to conduct exploratory analyses of the comparisons which are estimated to have small ESs (0.20-0.38): Diet vs. Control, PRT vs. Control and Combined vs. Gait.

Eligibility and recruitment

Participants are community- dwelling persons aged 40 or above, with medial knee OA in at least one knee according to the American College of Rheumatology clinical and radiographic criteria; and have a BMI $\geq 25\text{Kg/m}^2$. Complete inclusion and exclusion criteria are listed in Table 2.

Participants are currently being recruited via Hospital and University intranet advertisements, targeted mail-outs (Arthritis NSW, Concord Hospital) SSWAHS Intranet Arthritis NSW Website, Specialist / GP referral, advertisements in local newspapers and seniors' magazines, brochures distributed to local medical practitioners and pharmacies, as well as social media. We predict that we will need to

screen approximately 2000 people in order to enrol 125 participants.

Screening Procedure

- ***Telephone Screen:***

Potential participants initially contact the research assistant by telephone. To assess participant eligibility for THE LO Study, a 30-minute telephone screening form is utilized. The questions on the form are designed to address inclusion and exclusion criteria as well as the participant's basic demographic and contact information, current medical history, medication and physical activity/exercise levels.

- ***Investigator Review:***

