In this study, gait retraining will be conducted in a motion analysis laboratory under the supervision of an exercise physiologist trained in biomechanics. We aim to reduce the peak KAM by 20% over time. For the supervised portion of the gait retraining intervention, participants will attend a one-hour gait retraining session every fortnight during one year. At the first session, they will be educated on the significance of joint loading, the KAM and the main objective of this study arm. A larger peak observed indicates greater loading placed through the medial “inner” compartment of the knee joint. The participants’ natural gait pattern and joint kinetics will be assessed at the initial session for target level of 20% load reduction to be set. Participants will undergo three-dimensional gait analysis using a force platform (model 9281, Kistler, Winterter, Switzerland) and 14 camera motion capture system (Eagle cameras, Cortex 5 software, Motion Analysis Corporation, USA). The motion of the affected lower limb will be tracked using 16 passive-reflective markers during habitual gait in order to evaluate the baseline early stance peak KAM, knee abduction moment (KAbM), mid-stance KAM, gait velocity and measure of pain. KAM and KAbM will be available graphically in real time using Kintools (Motion Analysis Corporation,

USA). Participants will be asked to “just walk” along the laboratory walkway with no instructions provided regarding a modified gait. Three trials will be captured. These variables will be used to monitor biomechanical progress throughout the year by the trainer.

As part of the second session, participants will be made aware of the range of gait modification strategies via a PowerPoint presentation and will be able to choose the modification to attempt first. Participants will then attempt to practice all gait modification strategies while walking in the laboratory. The trainer will aid skill acquisition by the provision of regular verbal feedback or visual feedback using a mirror. Standardized instructions will be provided to them and each strategy will be systematically tested. Their trials will be recorded and their knee kinematics will be monitored until an optimal benefit is reached based on peak KAM reduction measured from the real time graphs.

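### The sample size assumes a 53% fall in peak KAM from gait retraining and calls it conservative, while the intervention aims for 20%; the protocol does not reconcile the two

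*Protocol*

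**What the plan says.** Protocol, Sample size estimation: "Gait retraining benefit is estimated as the average of effects achieved in the literature". The values are −65% from one published study, then "2007 (-39%) [17, 29] and in our pilot 4-week trial (-55"%). The average itself is not printed. The section admits limits ("We acknowledge potential imprecision due to the fact that these published trials included only healthy participants", and a pilot of 10 people with OA over 4 weeks) but concludes: "However, as THE LO study is 12 months rather than 4 weeks in duration, we believe our estimate is conservative".

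The same section gives the design parameters ("The sample sizes (n) required with alpha 0.05 and beta at 0.2 for each of the treatment arms is shown in Table 1") and the effect sizes: "Gait vs. Control (ES= 1.25) and Combined vs. Control (ES= 1.63"), plus 1.30 for Combined vs Diet and 1.43 for Combined vs PRT. Gait vs Control fixes 12 per group. That makes 60 completers, 100 recruits at 40% dropout, and 125 after 25 more are added for heterogeneity.

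Protocol, Interventions, Gait Retraining: "We aim to reduce the peak KAM by 20% over time". The first session assesses natural gait "for target level of 20% load reduction to be set".

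**The concern.** Both figures describe the change in peak KAM under the same gait retraining. The sizing figure is 53/20 = 2.65 times the aim, so a group that exactly met its target would show 20/53 = 38% of the planned effect. An assumption that far above the intervention's own aim cannot be called conservative without an explanation. The longer duration, which is the reason offered, does not explain the gap, because the 20% aim covers the same year.

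The statement that the study is powered for four comparisons depends on the larger figure. If gait retraining does what it sets out to do and no more, a non-significant Gait vs Control result becomes likely. It could then be read as evidence of no effect from an adequately powered trial.

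**Working it through.** **1. The protocol's own figures.** Two-sided alpha 0.05, power 0.80 and ES 1.25 give 11.09 per group by the two-sample t-test, rounded up to 12. Sidedness is not stated, but two-sided reproduces the 12. Then 5 × 12 = 60 and 60/(1 − 0.40) = 100. Both figures match the protocol.

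**2. The gait term.** (65 + 39 + 55)/3 = 53%.

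**3. Does 53% produce the stated effect sizes?** Baseline KAM (B) and SD are not in the available text, so I solved for them.
- Diet change: 8.9 kg × 0.496 = 4.41 Nm. Control change: 1.1 × 0.496 = 0.55 Nm.
- Combined is set as Diet plus Gait, so the Diet term is 1.63 − 1.25 = 0.38, and SD = 4.41/0.38 = 11.6 Nm.
- Gait vs Control: (0.53B − 0.55)/11.6 = 1.25, so B = (14.5 + 0.55)/0.53 = 28.4 Nm and B/SD = 2.45.
- Check, Diet vs Control: (4.41 − 0.55)/11.6 = 0.33, which equals 1.63 − 1.30.
- Check, PRT vs Control at the assumed 10%: (2.84 − 0.55)/11.6 = 0.20, which equals 1.63 − 1.43 and is the bottom of the printed 0.20–0.38 range.

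Other routes through the protocol's inputs, including its 1.4% per kg, give SD of 11.6 to 14.6 Nm and baseline of 28 to 35 Nm. B/SD stays at 2.43 to 2.45, and only this ratio is used below.

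**4. Replace 53% by 20%.** Each powered comparison contains the gait term once, so each loses (0.53 − 0.20) × 2.45 = 0.81. Rounding of the inputs moves the results by about 0.01.

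**5. Power.** Two-sided t-test, 2n − 2 degrees of freedom, noncentrality ES × √(n/2). Completers per arm: 25 × 0.60 = 15 at the planned dropout; 25 × (1 − 0.097) = 22.6 at the dropout reported in Discussion and Conclusions; 25 with none.

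| Comparison | ES at 53% | ES at 20% | Power, n = 15 | n = 22.6 | n = 25 | n per arm for 80% |
|---|---|---|---|---|---|---|
| Gait vs Control | 1.25 | 0.44–0.45 | 22% | 31% | 34% | about 80 |
| Combined vs Control | 1.63 | 0.82 | 59% | 77% | 81–82% | 24–25 |
| Combined vs Diet | 1.30 | 0.49 | 26% | 37% | 40% | 65–66 |
| Combined vs PRT | 1.43 | 0.62–0.63 | 38% | 54% | 58% | 41–42 |

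**6. Smallest gait reduction detectable with 80% power, Gait vs Control.** The control change in SD units is 0.55/11.6 = 0.047.
- At 15 per arm the detectable ES is 1.06: (1.06 + 0.047)/2.45 = 45%.
- At 22.6 per arm it is 0.853: (0.853 + 0.047)/2.45 = 37%.

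**7. Lowest cited effect, 39%.** Gait vs Control ES is 1.25 − 0.14 × 2.45 = 0.91. Power is about 57% at 12, 67–68% at 15 and 85% at 22.6 per arm.

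**The case against.** The strongest objection is that 20% is a training target, neither a ceiling nor a predicted group mean. The Gait Retraining section also has the trainer look for an optimal benefit and has participants repeat whichever strategies reduced peak KAM most. A reader might infer that 80% power is simply not delivered; the protocol does not support that, because it never says the mean will settle at 20%. This stands, and the power loss must be stated as conditional. It does not explain why the plan expects 2.65 times its aim.

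Other points:
- **The evidence is disclosed.** The 55% comes from the team's own pilot in people with OA, and the limits are admitted. True, but admitting imprecision does not make the figure conservative.
- **There is margin.** At 22.6 completers per arm the detectable reduction of 37% lies below all three source values. True at the reported dropout; at 15 per arm it is 45%, above the 39%. The extra 25 participants were added for heterogeneity, not for a smaller effect.
- **The analysis may be adjusted.** The powers above are for an unadjusted comparison. Adjusting for baseline divides the ES by √(1 − r²). With an assumed baseline–follow-up correlation of 0.7, 0.8 or 0.9, Gait vs Control power at 20% and 22.6 per arm is about 53%, 68% or 92%. No correlation is given, so this shows a way to recover power, not that it is recovered.
- **Combined leaves out PRT.** Adding the assumed 10% (0.10 × 2.45 = 0.245) to 0.82 gives Combined vs Control ES 1.07 and about 94% power at 22.6. This is a fair cushion for that comparison, but it does nothing for Gait vs Control.

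A reader might also infer that the 8.9 kg diet assumption contradicts the diet arm's 5–10% weight goal. It does not: 8.9 kg lies within 5–10% for anyone weighing 89 to 178 kg, and the cohort's mean weight is not given.

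**Conclusion.** The protocol plans on 53% and aims for 20% for the same outcome and intervention, without reconciling them, and the description as conservative is not supportable as written. This is a fault in the effect assumption, not in the arithmetic.

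The claim to be powered for four comparisons holds near 53%. At a mean effect near 20%, three of the four miss 80% power even if all 25 per arm complete, and Combined vs Control reaches it only with almost no dropout.

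These figures rest on a back-solved B/SD of about 2.45, an unadjusted two-sided t-test at 0.05, and a mean effect near the target. Which of the two percentages is right is not judged here.

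**What to change.** - Reconcile Sample size estimation with Gait Retraining: state how the 20% target relates to the mean effect expected at 12 months.
- Remove the description of the gait estimate as conservative.
- Print the 53% average, and restate the four effect sizes and their power at 20% beside the 39% and 53% scenarios.
- State the smallest gait reduction detectable with 80% power at the expected number of completers (about 45% at 15 and 37% at 22.6 per arm).
- If baseline adjustment is cited as recovering power, give the correlation and mark it as an assumption.

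The cost is a rewritten sample size paragraph and a less favourable stated power. No extra participants or data are needed.

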Individual counselling sessions will be conducted by the study dietitian to identify current dietary patterns, recommend specific changes, identify barriers to dietary changes and provide appropriate strategies to assist changes in behaviour with the participants. Nutrition counselling will incorporate a combination of behavioural theory, cognitive behaviour and trans-theoretical model in modifying dietary patterns, weight and health risks [46-49]. This will be accomplished with individual sessions with the dietitian once per week for the first month, then fortnightly for the next 2 months, then monthly for the final 9 months for a total of 17 sessions. The majority of the nutrition educational materials will be delivered during the first 12 weeks, with information on energy restriction, high protein and low GI addressed within the first 4 weeks and reiterated during sessions thereafter in combination with addressing behaviour modification. The study dietitian will also be available for telephone counselling and email queries outside of scheduled visits for additional support if required. Participants will be provided with a comprehensive written manual explaining all aspects of the diet, including sample meal plans. To further encourage dietary adherence, key foods will be provided in the form of a hamper (sample bag) and food, to give examples of low GI choices available [45].

All participants will have their waist circumference taken and will be weighed at each

diet visit using the same calibrated scale at the laboratory. In addition, participants will be instructed to record their weight at home daily, measure their waist circumference weekly and complete a weekly 24-hour food diary in a pocket-sized logbook provided at the beginning of the program. Regular self weighing and monitoring has previously been shown to encourage and significantly enhance compliance and weight loss efforts [50, 51]. Participants' logbooks will be reviewed at each visit or phone calls will be made to ensure compliance and to address any problems or concerns encountered by the participant. Additionally, 24-hour dietary recalls will be conducted during diet appointments in conjunction with completion of 3-day food records at baseline, 6 months and 12 months to assess and monitor dietary compliance.

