Participants identified to have renal impairment or proteinuria unrelated to urinary infections requiring limitation to protein intake will not be prescribed the higher protein diet. However, they will be advised to follow a low GI, reduced energy diet prescription and a referral to a nephrologist will be recommended.

- ***Combined Group***

Participants assigned to this group will receive a combination of all the components of gait retraining, high intensity PRT and HP/ low GI energy restricted diet interventions. The visits to the campus will be offered in combined sessions to minimise the burden in this group; thus, participants will attend 104 visits (2 days per week during 12 months) with 61 visits for PRT only (60 min approximately), 17 sessions for PRT and diet consultation (120 min approximately) and 26 for gait

retraining plus PRT (120min approximately). Gait retraining will be conducted prior to PRT when they occur on the same visit to minimise fatigue. Adequate rest periods will be provided between all intervention components.

- ***Control Group***

Participants in the Lifestyle Advice Control group will receive standard healthy eating and physical activity advice accompanied by written pamphlets. General lifestyle advice will be given at one education session by a trainer and participants will have the opportunity to ask any questions through their weekly phone calls. Dietary advice will be based on the Australian Guide to Healthy Eating [44], including information on recommended serves of food each day (e.g. breads and cereals, fruit, vegetables, dairy, meat and alternatives) as well as serving sizes and healthier choices for certain foods (e.g. low fat dairy products, lean meats). No specific energy or macronutrient distributions will be set for this group, however the Australian Guide to Healthy Eating reflects macronutrient distributions of 15-21% protein, 52-57% carbohydrate and 27% fat [25]. In addition, there will not be a specific weight loss target set for these participants throughout the study period, though weight loss will not be discouraged. Physical activity advice will be based on the Australian Government's National Physical Activity Guidelines of at least 30 minutes of activity on most days of the week. [11] No structured or supervised exercise will be provided.

Adverse Events

Adverse events will be monitored by a weekly questionnaire, provided in person or by

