telephone call, and proxy information obtained whenever necessary to minimise missing data. Additionally, participants will be requested to report all changes in medication, health care professional visits, new diagnoses, acute illness or allergies, changes in daily physical activities or any new symptoms. Any musculoskeletal, cardiovascular event or metabolic abnormality attributed to study protocols will be considered as adverse events [52]. Case conferences will be held weekly to discuss all study participants in terms of adherence, changes in health status, intervention modifications, adverse events and behavioural issues that were deemed relevant to study participation.

OUTCOME MEASURES

Participants will be assessed at baseline, six months and 12 months (immediately after completion of one-year program) by blinded outcome assessors. Blinding of participants is not possible due to the nature of the interventions.

Primary outcome

Peak KAM during the early stance phase of gait will be obtained in three-dimensional analysis laboratory. Data will be collected using a 14-camera Motion Analysis system (Eagle cameras, Cortex 5 software, Motion Analysis Corporation, USA) synchronised with three force plates (model 9281, Kistler instruments, Switzerland) embedded in the laboratory floor. Spatiotemporal, kinematic and kinetic will be computed from inverse dynamics analysis of an eight-segment body model defined by 30 markers over anatomical landmarks on the trunk, pelvis and lower limbs. The maximum KAM

between heel contact and 50% of stance will be derived and normalised to body weight times height ($Bw \cdot Ht$). The early stance peak KAM has been shown to be highly reproducible, with a mean difference between test sessions of 0.1%. This biomechanical analysis will be used to assess secondary gait variables, including the KAM impulse, KAM late stance peak, peak knee flexion moment, cadence, velocity, step length, kinematics of the ankle, knee and hip.

Secondary outcomes

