[^] Identified by the study physician as the more affected knee with medical knee OA after reviewing radiographs and doing physical examination.

Table 2. Details on visit for the testing and training sessions

	LIFESTYLE GROUP	DIET GROUP	GAIT GROUP	PRT GROUP	COMBINED GROUP
Assessment sessions	3	3	3	3	3
(Number of time points)	Baseline	Baseline	Baseline	Baseline	Baseline
	6 months	6 months	6 months	6 months	6 months
	12 months	12 months	12 months	12 months	12 months
Training sessions	1 visit	17visits	26visits	104 visits	104 visits
(12 months)	At the beginning of the study	1 st month: once weekly 2 nd & 3 rd month: once fortnightly 4 th and further: once monthly	One fortnightly session	Two weekly sessions	61 PRT sessions only 17 PRT + diet sessions 26 PRT + Gait sessions
Health Status Check	Weekly: All by telephone call, emailed or posted.	Weekly: During the training period, these will be done in person.	Weekly: During the training period, these will be done in person.	Weekly: During the training period, these will be done in person.	Weekly: During the training period, these will be done in person.

Table 3. Progressive Resistance Training Exercise Modification

Exercise	Difficulty/Symptom	Modification	Instructions And Feedback
Knee Extension	Patello-femoral pain	Isometric contraction against static resistance Hold for 10 seconds (1 repetition) If unable, hold as long as possible Repeat 23 or 15 repetitions If pain is still present: Do sub-Max isometric contractions.	Alternate legs. 10 seconds rest between contraction Observe effort and ask patient to visualize pushing against the bar as hard as they can. Place the participant's hand on their muscle in order for them to ascertain how the muscle feels when they are performing at a maximum effort.
	Shin pain	Extra padding on padded bar	No pain or pressure
	Baker's Cyst (swelling behind the knee joint)	Sit further forward on the seat Minimal contact or pressure behind the knee at the seat Extra pad behind the knee,	
Hip Machine	Pain (during eccentric phase)	Start at 80 degrees and perform the eccentric phase slowly	
	Knee pain	Move roll bar higher up thigh to avoid touching the knee	No pain
	Hip pain	Isometric contraction against static resistance	No pain
	Vertigo	Hold for 10 seconds (1 repetition) Repeat 15 or 23 repetitions Use ankle cuffs Perform the abduction and/or adduction lying prone on a plinth Can perform hip abduction lying on the side	

Table 4. Secondary outcome measured

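### The adverse-event definition requires attribution to the study protocol, so labelled adverse events are likely to be biased towards the active arms; Table 2 also conflicts with the text on how events are collected

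*Protocol*

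**What the plan says.** The Adverse Events section makes three statements that matter here.

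- Collection: "Adverse events will be monitored by a weekly questionnaire, provided in person or by" telephone, with "proxy information obtained whenever necessary to minimise missing data". No mode is tied to an arm.
- Scope of reporting: "participants will be requested to report all changes in medication, health care professional visits, new diagnoses, acute illness or allergies", and also changes in daily activity and any new symptom. This is limited neither by arm nor by cause. Weekly case conferences then review every participant.
- Definition: "Any musculoskeletal, cardiovascular event or metabolic abnormality attributed to study protocols will be considered as adverse events".

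Table 2 (visit details) gives the mode of the weekly health check by arm. For the lifestyle (Control) arm it is "Weekly: All by telephone call, emailed or posted". For Diet, Gait, PRT and Combined it is "Weekly: During the training period, these will be done in person".

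On exposure, the Control Group section says "General lifestyle advice will be given at one education session by a trainer", with no supervised exercise. Table 2 lists 17 training visits for Diet, 26 for Gait and 104 each for PRT and Combined. All arms share three assessment sessions.

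On blinding, the Randomisation section says that trainers are told the allocation and assessors are blinded. Outcome Measures says that participants cannot be blinded. Nothing states who attributes events.

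**The concern.** Relatedness is usually recorded beside an event. Here it decides whether the event exists in the adverse-event count. An event can be attributed to study procedures only to the extent that the participant has undergone some, and the arms differ greatly in that respect. The same knee-pain flare could be an adverse event in a participant who trained that week and an unlabelled symptom in a Control participant.

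The rule can also fail in the other direction. A real harm of gait retraining or resistance training that staff ascribe to the participant's osteoarthritis drops out of the count.

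The safety account of the trial is at stake. The protocol calls gait retraining and the combined programme its most novel interventions, and it claims conformity with CONSORT, so a harms table by arm is a natural product. The primary analysis of the knee adduction moment is not affected.

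**Working it through.** The protocol states no harms figure to reproduce. The check compares the passages and counts visits.

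**1. Does the label depend on arm?** Scheduled contact after allocation, from Table 2 and the intervention sections:

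| Arm | Training visits | Assessments after baseline |
|---|---|---|
| Control | 1 | 2 |
| Diet | 17 | 2 |
| Gait | 26 | 2 |
| PRT | 104 | 2 |
| Combined | 61 + 17 + 26 = 104 | 2 |

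The first of the three common assessments precedes randomisation. The assessments include maximal strength tests and a rapid stair climb (secondary outcomes table), so Control has some procedures to which an event could be attributed, but far fewer than PRT or Combined.

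**2. How far could the label move the comparison?** The inputs below are assumptions, except the arm size: 125 / 5 = 25.

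Labelled events = arm size × true risk × share attributed.

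- Active arm, true risk 40%, half attributed: 25 × 0.40 × 0.50 = 5.0.
- Control, same true risk, with 0%, 10%, 25% or 50% attributed: 0, 1.0, 2.5 or 5.0.
- With true risk from 20% to 60%, the active arm gives 2.5 to 7.5. Control gives 0 if nothing is attributed, and the same 2.5 to 7.5 if half is.

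With no true difference, the result runs from no bias to a complete contrast, depending on a quantity that the protocol leaves uncontrolled.

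**3. Can Table 2's collection mode be met?** Diet: weekly for one month, fortnightly for two, "then monthly for the final 9 months for a total of 17 sessions", so 4 + 4 + 9 = 17. The most weekly checks that can fall on a training visit:

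- Diet: 17/52 = 33%, leaving 35 weeks without a visit.
- Gait: 26/52 = 50%, leaving 26 weeks.
- PRT and Combined: two visits a week, 52/52 = 100%.
- Control: 0% by design.

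Weekly in-person checks therefore do not fit the Diet and Gait schedules. Email and post appear only in Table 2; the Adverse Events text allows only in-person or telephone contact.

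**4. What would a mode difference do?** If remote checks captured between 100% and 60% of what in-person checks capture (an assumption), equal risks would appear as a ratio of 1/1.0 = 1.0 to 1/0.6 = 1.67. Nothing in the protocol says where in that range, or outside it, the trial lies.

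**The case against.** The strongest reply is that only the label is restricted, not the data. The sentence before the definition asks participants to report symptoms, diagnoses, illness and health-care contacts whatever the cause, every arm is checked weekly, and every participant is discussed weekly. This stands. A reader might infer that harms cannot be compared between arms at all; the protocol does not support that, because an all-cause comparison can be built from these reports.

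A reader might also infer that Control will look almost free of events. That is not shown either. Control undergoes the same demanding assessments and is advised to be physically active, so its attributed share need not be zero. An illustration that sets it to zero is only one end of the range.

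Third, the protocol does not say that attribution is made with knowledge of the arm. That is an inference: trainers and participants know the arm, and judging whether study procedures caused an event ordinarily requires knowing which procedures the participant had. It is a reasonable inference, not a stated fact.

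On mode, a clean split between Control and the active arms exists only in Table 2's wording. Diet and Gait probably have many remote checks, since the Adverse Events text allows telephone and the diet section mentions phone calls. Table 2 may mean only that checks are in person when a training visit occurs, but it then gives no mode for the remaining weeks.

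Finally, no hypothesis concerns harms, and tabulation may be left to an analysis plan. That does not answer the point about the definition, which the protocol itself fixes.

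**Conclusion.** The concern holds for labelled adverse events. Their comparison between arms is likely to be biased towards more events in the active arms, and harms ascribed to the underlying disease are omitted. This rests on reading the single definition sentence as exclusive, and on attribution not being blinded, which the protocol neither states nor rules out. The magnitude cannot be derived; under the assumptions above it runs from none to 5.0 against 0 labelled events.

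The mode point holds in part. Table 2 disagrees with the Adverse Events text and, for Diet and Gait, with its own visit counts (33% and 50% of weeks at most). Mode therefore varies among the active arms as well as against Control. The effect on capture cannot be estimated from the protocol.

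The point deserves correction before harms are reported. It does not touch the primary outcome.

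**What to change.** 1. Define an adverse event as any new or worsened event, in any arm, regardless of cause.
2. Record relatedness to study procedures as a separate field, assessed blind to arm where feasible, and state who assesses it.
3. Tabulate all-cause and related events by arm.
4. Recode the weekly reports already collected under the new definition.
5. Reconcile Table 2 with the Adverse Events text and the visit schedule, including whether email and post are used. Record the mode of each check, where known for past checks, and state the mode difference as a limitation of the harms comparison.

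The cost is some recoding. The definition change needs no new data, since the reports are already requested.

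Moving every arm to one remote mode is a weaker remedy. For PRT and Combined it could mean up to 2 × 25 × 52 = 2,600 contacts over the whole trial. Recruitment is stated to be 80% complete, so it could not reach checks already done. Trainers would still see those participants twice a week and hear of symptoms.
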